- 1) Test the health impact of CGM of inpatients as defined by rates of hypo- and hyperglycemia and the derivative of time in appropriate glucose range. Forty (40) patients will be randomized 1:1 into one of two groups. In the treatment group, patients will receive a Dexcom G6 device and the clinical staff (i.e., nursing and medical staff assigned to the patient's care) will be trained to use readings from the Dexcom G6 for the management of the patient's glucose levels below 100. In the control group, patients will receive a Dexcom G6 PRO device, but the clinical staff (i.e., nursing and medical staff assigned to the patient's care) will not have access to the readings and will provide usual care (four glucose checks per 24 hours and use of insulin or other diabetic agent ordered by the admitting and rounding providers to determine glucose management).
 - a. Hypothesis 1: Patients in the treatment group will experience fewer episodes of hypoglycemia as compared to patients in the control group as measured by the Dexcom device readings.
 - b. Hypothesis 2: Patients in the treatment group will experience less frequent hyperglycemia events as compared to patients in the control condition as measured by the Dexcom device readings.

Approach

Subject Recruitment & Enrollment Plan: Non-surgical, non-ICU patients with diabetes admitted to BSWMC-Temple who meet the inclusion/exclusion criteria delineated below will be approached for enrollment within 24 hours of admission. Screening and enrollment will be conducted by a research nurse or a Clinical Research Coordinator with consents signed for those wanting to participate.

Inclusion Criteria:

- Patients with Type 1 and Type 2 diabetes.
- Subjects 18 years of age or older with diabetes.
- Subjects willing to avoid using high dose acetaminophen (defined as greater than 4 gm per day)
- Subjects with expected hospital length-of-stay of 2 or more days.

- Subjects willing to wear CGM device.

Exclusion Criteria:

- Female subjects who are pregnant or lactating at the time of enrollment into the study. Females with childbearing potential will be queried about the possibility of pregnancy and a serum pregnancy test will be performed.
- Subjects with greater than 4gm use of Tylenol/24 hr.
- Surgical patients or patients with pre-planned surgery during the study.
- Subjects with acute illness admitted to the ICU or expected to require admission to the ICU.
- Patients who may potentially require IV insulin.

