- All unexpected adverse device events, (UADEs), ADEs, device complaints, and device malfunctions will be reported irrespective of whether an adverse event occurred.

Criteria for Discontinuation of Individual Participants:

Subjects can decide to discontinue entirely from the study at any time for any reason. This is documented as withdrawal of consent. Subjects can also be discontinued from the study or discontinued from the study treatment due to Investigator or Sponsor decision as detailed below.

1. Withdrawal of consent.
2. At the Investigator's discretion in certain situations such as lack of compliance or serious adverse event. (A single severe hypoglycemic event resulting in seizure or LOC or DKA).
3. 2 or more hypoglycemic events based on CGM readings that do not correlate with standard finger stick blood glucose monitor readings.
4. One DKA event or one episode of hyperglycemic, hyperosmolar nonketotic syndrome (HHNS).
5. Skin infection at the site of device insertion that occurs after placement of the device.
6. Transfer of the patient to the ICU or deterioration of medical condition that in the judgment of the principal investigator carries an unacceptable risk for the participant.
7. Skin irritation at the site of device insertion prompting the patient to request removal of the device.

Criteria for stopping the overall study:

1. The IRB will have the responsibility of determining if the overall study should be stopped. Each participant withdrawal (except withdrawal of consent) will be reported to the IRB within 3 days.
2. If an investigational device malfunction results in an SAE and the issue cannot be corrected by a modification to the system or a component of the system or adjustment to protocol procedures, the study will be stopped.
3. In the case of unanticipated adverse device effects (UADEs) related to a severe adverse event, the study will be stopped while the severe adverse event is evaluated and a root cause is determined by the Sponsor.

Randomization:

Patients that meet enrollment eligibility and consent to participate in the RCT will be randomized 1:1 to one of two groups, treatment or control using Research Electronic Data Capture (REDCap).

Randomization will be performed by assigning computerized random numbers. Computerized random numbers will be generated by statistical software.

Application of the Dexcom Devices:

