Following randomization, the clinical nurse researcher will return to the patient's bedside to apply the Dexcom G6 or Dexcom G6 PRO sensor and transmitter. The sensor can be placed on the upper arm or abdomen. Those in the treatment group will then link the transmitter to the receiver. All clinical nurse researchers assigned to this project will be trained on the application of the device according to Dexcom protocol. The clinical nurse researcher will calibrate the device according to Dexcom protocol.

In some cases, patients will experience care procedures that require the device to be temporarily or permanently removed. If a patient requires a CT, the device will remain in place. If a patient requires an MRI as part of routine evaluation during hospitalization, the CGM device will be removed prior to imaging and a new one will be placed within twelve hours of the patient returning to their patient room on the nursing floor.

Dexcom sensors may be worn up to 10 days. The sensor will only be replaced if it is not providing appropriate readings or as noted above.

Standing Order for All Patients Enrolled in the Study:

Attending and/or consulting physicians will be responsible for writing orders for finger stick glucose measurements on all patients per standard care whether they are in the treatment or control group. Insulin orders will be determined by the patients' home medication history and current clinical status. To avoid investigator bias, orders written by the attending will not be adjusted by the study team with the exception of standing orders for nurse response to CGM readings as detailed below for those patients randomized to the treatment group. Standing orders for blood sugars <100 will allow for administration of glucose replacement in the treatment group based on Dexcom G6 reading.

CGM informed Clinical Care (Treatment Group):

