Glucose management of patients in the treatment group will be guided by readings from the Dexcom G6. The Dexcom device will provide interstitial fluid glucose measurements at five-minute intervals used to construct a graph for trending CGM levels as well as an approximate rate of change. Threshold alarm for hypoglycemia will be set with CGM glucose values < 100 mg/dL and system alarm for CGM glucose value < 55 mg/dL. The alarms will be incorporated into the decision protocol for treatment of low blood glucose levels to achieve the stated goal of improved glycemic control and decreased rates of hypoglycemia within the hospital setting.

This requires a detailed protocol of how the devices is to be used in the RCT and that all clinical staff assigned to the patient be trained to follow the protocol (i.e., staff must be trained to use CGM as a patient care tool).

The Dexcom G6 protocol includes the following:

- 1) The treatment group will have the data displayed with alarms set for glucose measurements of
 - A. Threshold alarm CGM glucose < 100 mg/dL
 - B. The urgent low soon alert, indicated by 2 downward arrows on the device reading. (Blood sugar of 55 mg/dL in less than 20 minutes)
 - C. Urgent low system alarm set at CGM glucose < 55 mg/dL.
- 2) Definition of target range is CGM glucose 100 -180 mg/dL
- 3) Definition of hypoglycemia is CGM glucose < 70 mg/dL (2 consecutive CGM readings below threshold)
- 4) Definition of hyperglycemia is CGM glucose > 300 mg/dL (2 consecutive CGM readings above threshold)
- 5) Definition of Severe hypoglycemia (see below)

Severe Hypoglycemia: the event required assistance of another person due to altered consciousness, and required another person to actively administer carbohydrate, glucagon, or other resuscitative actions. This means that the subject was impaired cognitively to the point that he/she was unable to treat himself/herself, was unable to verbalize his/her needs, was incoherent, disoriented, and/or combative, or experienced seizure or coma. These episodes may be associated with sufficient neuroglycopenia to induce seizure or coma. If plasma glucose measurements are not available during such an event, neurological recovery attributable to the restoration of plasma glucose to normal is considered sufficient evidence that the event was induced by a low plasma glucose concentration.

Definition of severe hyperglycemia/DKA:

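### Removal for CGM lows that fingersticks do not confirm can, as described, happen only in the treatment arm, while unconfirmed CGM lows count toward the primary outcome in both arms

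*Protocol*

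**What the plan says.** Protocol, Criteria for Discontinuation of Individual Participants, item 3, lists as a ground "2 or more hypoglycemic events based on CGM readings that do not correlate with standard finger stick blood glucose monitor readings". The lead-in says subjects can be "discontinued from the study or discontinued from the study treatment due to Investigator or Sponsor decision", so removal is discretionary and may mean leaving the study or only the study treatment. No arm is named.

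The arms differ in who sees CGM values:

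- **Treatment.** Application of the Dexcom Devices: "Those in the treatment group will then link the transmitter to the receiver". Dexcom G6 protocol, item 1: "The treatment group will have the data displayed with alarms set for glucose measurements of" specified thresholds. Research Blood Glucose Protocol, step xi, requires a fingerstick check of any CGM value below 70 mg/dL.
- **Control.** Under the Aim, staff "will not have access to the readings and will provide usual care". No CGM-triggered fingerstick is described.

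The Combined protocol and SAP links a receiver for every enrolled patient, but it too withholds control readings from clinical staff and describes no control-arm check.

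Hypothesis 1 predicts "fewer episodes of hypoglycemia as compared to patients in the control group as measured by the Dexcom device readings". An episode is two consecutive CGM readings below 70 mg/dL, with no fingerstick confirmation. Data Analysis makes the number of hypoglycemic events a primary measure, tested by t-test, or by a Wilcoxon-type test if normality fails. Outcome Measures uses device time as the denominator and excludes patients with under 48 hours of readings.

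On faulty sensors: "The sensor will only be replaced if it is not providing appropriate readings" (or after certain procedures). Physicians are responsible for "writing orders for finger stick glucose measurements on all patients per standard care whether they are in the treatment or control group", yet Table 1 lists no fingerstick values.

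**The concern.** Item 3 can operate only if someone sees a CGM low and compares it with a fingerstick while the patient is still on study. As described, only the treatment arm has that pathway. A sensor that reads falsely low can end device time there after two unconfirmed lows. In the control arm the same sensor stays on and each false low is counted. If the treatment patient is removed within 48 hours, that patient also leaves the analysis.

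This is selection by arm on the error in the outcome measure. It can produce a difference in a primary outcome when CGM-guided care does nothing. With no removals reported by arm and no sensor-independent measure, a reader could not tell how much of a difference is sensor artefact.

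**Working it through.** The plan gives no event rate, false-low rate or effect size, so it has no figure to reproduce here. The only stated number is 40 patients, 1:1, and the point does not depend on it.

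**Step 1. Does the rule work the same way in each arm?**

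| What item 3 needs | Treatment | Control |
|---|---|---|
| CGM low visible during the stay | Yes: receiver, display, alarms | Withheld from clinical staff |
| Fingerstick prompted by that low | Yes: step xi | None described |
| CGM low counted in the outcome | Yes | Yes |

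If the rule ran identically in both arms, or in neither, the arms would be exchangeable under no effect and the expected ratio would be 1.00.

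**Step 2. Assumptions (none from the documents).** True lows 0.3/day in both arms. A share *p* of sensors is prone and gives λ false lows/day; the rest give 0.05/day. Wear is uniform over 2–10 days. Removal is at the second false low, treatment arm only, with probability 1.0 or 0.5. There is no true effect.

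**Step 3. Treatment patients lost to the 48-hour exclusion.** With Poisson false lows and certain removal, the chance that the second comes before day 2 is 1 − e^(−2λ)(1 + 2λ):

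- λ = 1.5: 1 − 0.0498 × 4 = 0.801
- λ = 2.0: 1 − 0.0183 × 5 = 0.908
- λ = 2.5: 1 − 0.00674 × 6 = 0.960
- λ = 0.05: 1 − 0.9048 × 1.1 = 0.005

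For *p* = 0.2, λ = 1.5, the loss is 0.2 × 0.801 + 0.8 × 0.005 = 0.164. The simulation gave 16%.

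**Step 4. How demanding are these scenarios?** The false share of control-arm lows is F/(F + 0.3), where F = pλ + (1 − p) × 0.05. For *p* = 0.2, λ = 1.5: F = 0.30 + 0.04 = 0.34, and 0.34/0.64 = 53%.

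**Step 5. Monte Carlo, 400,000 patients per arm, certain removal, 48-hour exclusion.** Ratios are treatment/control; the truth is 1.00.

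| *p*, λ | False share, control | Lost to 48 h | Pooled rate | Mean patient rate | Mean count |
|---|---|---|---|---|---|
| 0.2, 1.5 | 53% | 16% | 0.57 | 0.60 | 0.55 |
| 0.2, 2.5 | 64% | 20% | 0.42 | 0.43 | 0.41 |
| 0.3, 1.5 | 62% | 24% | 0.48 | 0.52 | 0.45 |
| 0.1, 2.0 | 45% | 10% | 0.64 | 0.66 | 0.63 |

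Pooled ratio under milder inputs:

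- same four scenarios, removal half the time: 0.74–0.84
- 10–20% of sensors at 1.0/day: 0.70–0.81
- 10–20% at 0.5/day: 0.88–0.93
- all sensors at 0.05–0.1/day: 0.98–1.00

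**Step 6. Direction.** Without the 48-hour exclusion, the four high-rate scenarios give 0.51–0.71 pooled and 0.41–0.64 for mean counts, but mean patient rates reverse to 1.38–1.61. Stopping at an event inflates a short patient's rate: two lows in 12 hours is 2/0.5 = 4 per day.

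**Step 7. False significance favouring CGM** (20 per arm, per-patient rates, 48-hour exclusion, nominal 2.5%).

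| Scenario | t-test | Wilcoxon |
|---|---|---|
| Four high-rate, always removed | 9.3–36.4% | 6.5–21.8% |
| Same, removed half the time | 4.5–9.4% | 4–7% |
| 10–20% of sensors at 0.5/day | 3.2–4.0% | not run |
| All sensors at 0.1/day | 2.1% | not run |
| No removal (check) | 2.2% | not run |

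**Step 8. A second model.** With true lows averaging 0.2/day, false lows varying smoothly between patients, certain removal and the 48-hour exclusion, the mean count ratio was 0.95–0.97 at 0.05 false lows/day and 0.49–0.58 at 0.4/day. Mean patient-rate ratios were 1.01 and 0.65–0.84. The pattern is the same: little distortion when false lows are rare, material distortion when they are common.

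**The case against.** - **One-sidedness is read from silence.** Item 3 names no arm, and the bar on readings covers clinical staff, not research staff. Controls have four glucose checks a day, and the combined document links their receivers, so an undescribed review could apply the rule to them. This stands as a limit on certainty. It does not remove the problem, because no such review is described.
- **The large ratios need harsh inputs.** In the high-rate scenarios 45–64% of control lows are false and 14–32% of the treatment arm is removed. Removal is certain although the rule is discretionary, and bad sensors are never replaced although replacement is allowed. This also stands; under mild inputs the effect nearly vanishes. The documents do not let a reader place the trial within the range.
- **The planned fallback test is less affected.** True, but 6.5–21.8% is still well above 2.5%.
- **The direction is not fixed, and the 48-hour exclusion contributes much of it.** Correct, which is why results are needed on both scales and with and without that exclusion.
- **Safeguards exist.** Withdrawals other than withdrawal of consent go to the IRB within 3 days, device malfunctions are reported, and severe hypoglycemia is defined clinically. None of these corrects the comparison of CGM-counted episodes, and severe events will be rare.
- **It is a feasibility pilot.** It still tests directional hypotheses, and its Benefits section says the findings could change standard care.

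**Conclusion.** The concern holds. As described, item 3 can act only in the treatment arm, on the same sensor errors that feed a primary outcome in both arms. With no true effect and the 48-hour exclusion, the pooled ratio could lie anywhere from about 1.00 (false lows rare) to 0.42 (10–30% of sensors badly prone and always removed). Under that exclusion the distortion usually favours CGM; without it, mean per-patient rates can point the other way. These figures rest on assumed false-low rates, wear times and removal probabilities. Confidence is medium because the one-sidedness is inferred from the described data flow and the false-low rate is unknown. It should be fixed, since at 20 per arm a few one-sided removals matter and the remedy is cheap.

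**What to change.** Leave the clinical rules as they are and change the data collection and analysis:

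1. Add scheduled pre-meal and bedtime fingerstick values from the EHR to Table 1 for both arms. Name hypoglycemia below 70 mg/dL on scheduled fingersticks as a supportive analysis of Hypothesis 1, by assigned arm and including all randomized patients. Leave out CGM-triggered fingersticks, which occur in one arm only.
2. Keep, by assigned arm, whatever CGM readings exist for patients discontinued under item 3. Show the primary hypoglycemia result with and without those patients, and with and without the 48-hour exclusion, both as counts and as events over device time.
3. Report by arm the item 3 removals and the sensor replacements for inappropriate readings.

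The sponsor must also reconcile how item 3 applies in the control arm and whether it means leaving the study or only the study treatment. No clinical rule is proposed here.

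The cost is one extra extraction of results already ordered in both arms, a few sensitivity tables and some analysis wording. The downside is precision: scheduled fingersticks detect fewer lows than CGM, so that analysis can only support the primary result.

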2. An Adverse Device Effect
3. An Adverse Event occurring in association with a study procedure
4. Hypoglycemia meeting the definition of severe hypoglycemia as defined below
5. Diabetic ketoacidosis (DKA) as defined below (#4) or in the absence of DKA, a hyperglycemic or ketosis event meeting the criteria defined below

Relationship of Adverse Event to Study Device

The study investigator will assess the relationship of any adverse event to be related or unrelated by determining if there is a reasonable possibility that the adverse event may have been caused by the study device.

To ensure consistency of adverse event causality assessments, investigators should apply the following general guideline when determining whether an adverse event is related:

- Yes. There is a plausible temporal relationship between the onset of the adverse event and the study intervention, and the adverse event cannot be readily explained by the participant's clinical state, intercurrent illness, or concomitant therapies; and/or the adverse event follows a known pattern of response to the study intervention; and/or the adverse event abates or resolves upon discontinuation of the study intervention or dose reduction and, if applicable, reappears upon re-challenge.
- No. Evidence exists that the adverse event has an etiology other than the study intervention (e.g., preexisting medical condition, underlying disease, intercurrent illness, or concomitant medication); and/or the adverse event has no plausible temporal relationship to study intervention.

Intensity of Adverse Event

The intensity of an adverse event will be rated on a three-point scale: (1) mild, (2) moderate, or (3) severe. It is emphasized that the term severe is a measure of intensity; thus, a severe adverse event is not necessarily serious. For example, itching for several days may be rated as severe, but may not be clinically serious.

- MILD: Usually transient, requires no special treatment, and does not interfere with the participant's daily activities.
- MODERATE: Usually causes a low level of inconvenience or concern to the participant and may interfere with daily activities but is usually ameliorated by simple therapeutic measures.
- SEVERE: Interrupts a participant's usual daily activities and generally requires systemic therapy or other treatment.

Reportable Device Issues

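### Stopping item 3 ties the automatic hold to a severe event rather than a serious one, so a serious UADE graded below severe triggers no hold unless item 2 applies

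*Protocol*

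**What the plan says.** Item 3 of Criteria for stopping the overall study (Protocol, with the same wording in the Combined protocol and SAP) deals with UADEs in these words: "related to a severe adverse event, the study will be stopped while the severe adverse event is evaluated and a root cause is determined"; the sponsor finds the cause.

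Under Intensity of Adverse Event, both documents fix the meaning of severe. The Protocol writes "It is emphasized that the term severe is a measure of intensity" and adds that "a severe adverse event is not necessarily serious". Its example is itching over several days, which may earn the top grade without being clinically serious.

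The neighbouring stopping items work differently:
- Item 2 is tied to seriousness but needs a further condition: "If an investigational device malfunction results in an SAE and the issue cannot be corrected" by changing the system, a component or the procedures.
- Item 1 is discretionary: "The IRB will have the responsibility of determining if the overall study should be stopped".

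The other relevant rules concern reporting or the individual participant:
- Under Reportable Device Issues, "All unexpected adverse device events, (UADEs), ADEs, device complaints, and device malfunctions will be reported irrespective of whether an adverse event occurred".
- Under Monitoring for Adverse Events and Serious Adverse Events, an SAE that is unexpected and definitely or probably related goes to the IRB at once, with a limit of three business days. Unanticipated adverse device events have an outer limit of 10 business days.
- The investigator may discontinue a participant "in certain situations such as lack of compliance or serious adverse event", and "Each participant withdrawal (except withdrawal of consent) will be reported to the IRB within 3 days".

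**The concern.** Item 3 is the only rule that automatically holds the study while the cause of an unanticipated device effect is sought. Its trigger is the intensity grade, although the same document warns that intensity and seriousness differ, and although item 2, directly above, uses the SAE term.

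Taken literally, the rule orders events oddly. An unanticipated device effect that is uncomfortable but not serious would halt the trial if graded severe. One that meets the SAE standard but is graded moderate would not. Both arms wear a Dexcom sensor, so an unexplained device harm could affect any later participant. At stake is whether enrolment and device wear can continue, at someone's discretion, while such an event is investigated.

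**Working it through.** **Step 1. Apply the three stopping items to each kind of UADE.**

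- *Severe and serious:* item 3 holds the study.
- *Severe, not serious:* item 3 holds the study.
- *Serious, graded below severe, no malfunction:* item 3 does not apply because the event is not severe. Item 2 does not apply because there is no malfunction. What remains is reporting and IRB discretion under item 1.
- *Serious, graded below severe, from a malfunction:* item 3 does not apply. Item 2 stops the study if the malfunction cannot be corrected, but provides no hold while that is being decided.

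The third and fourth cases make up the gap. They require that an event can be serious without being severe. The documents state only the converse; this direction is inferred from intensity being a separate scale. The available text does not define UADE, but the gap does not depend on the definition, because item 3 adds the severity condition to whatever counts as one.

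**Step 2. Bound the reporting delay.** The plan gives no figure to reproduce and no UADE rate.

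Inputs:
- 40 patients (AIM).
- Reporting limits of 3 and 10 business days (Monitoring for Adverse Events and Serious Adverse Events).
- Even enrolment over 3 to 12 months. This is an assumption: the 12-month Study Timeline in the Combined protocol and SAP does not show which months are for enrolment.

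Counting from each day of the week and ignoring public holidays, 3 business days is 3 to 5 calendar days and 10 business days is 12 to 14.

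Further patients enrolled = (40 / enrolment days) × calendar days:
- 3-business-day limit, low: 40/365 × 3 = 0.3.
- 3-business-day limit, high: 40/(365/4) × 5 = 2.2.
- 10-business-day limit, low: 40/365 × 12 = 1.3.
- 10-business-day limit, high: 40/(365/4) × 14 = 6.1.

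**Step 3. Decide which limit applies.** A serious UADE is an unexpected SAE attributed to the device, so the three-business-day limit would normally govern, giving 0.3 to 2.2 patients. The longer limit matters only if relatedness is judged below probable. That possibility is real but secondary: the Protocol's causality section offers only related or unrelated, so its scale does not map directly onto definite or probable.

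**The case against.** The strongest objection is that the gap is nearly empty. The severe grade covers events that interrupt usual activities and generally need treatment, while moderate means low-level inconvenience or concern. Most events bad enough to be SAEs would therefore be graded severe and caught by item 3. The foreseeable device harms (skin irritation, infection, bleeding, inaccurate values) are already listed under Anticipated Challenges, so they are hard to call unanticipated. This stands, and it limits how often the gap could matter. It does not make the wording right.

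Second, safeguards remain: reporting of every UADE and malfunction, IRB stopping power, discontinuation of the affected participant, and freedom for the study team to pause sooner. This also stands, but these are duties to report or matters of discretion. Discontinuing one participant does not protect the others.

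Third, the enrolment figures are soft. The limits are ceilings on reports due at once or as soon as possible. Item 3 itself takes effect only after someone learns of the event, classifies it and grades it. The counts are patients enrolled, not patients harmed. All of this is accepted.

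Three stronger readings are tempting, and the documents support none of them:
- *A serious UADE below severe can never stop the trial automatically.* Item 2 stops it at any intensity when an uncorrectable malfunction caused the SAE.
- *Up to 6 more patients would typically be enrolled.* That figure needs the 10-business-day limit, which does not normally govern an unexpected, device-related SAE.
- *The trial is unsafe or its results are compromised.* Nothing in the documents shows an expected event in the gap, and no outcome or analysis depends on item 3.

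**Conclusion.** The point holds as a narrow defect in a safety rule. As worded, item 3 leaves without an automatic hold a UADE tied to a serious event graded below severe, except where item 2 applies. It does hold the study for a severe but non-serious UADE. Whether *severe* was deliberate or a slip for *serious* cannot be settled from the documents; both carry the word and neither corrects it.

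The practical size is small. About 0.3 to 2.2 further patients could enrol by the normal reporting limit, given even enrolment over an assumed 3 to 12 months and nobody pausing at discretion. This is an upper bound on the reporting delay alone; the time the IRB then takes to act is not stated. Patients already wearing a sensor are not counted. The conclusion also rests on the inference that serious need not mean severe. The efficacy analysis is unaffected.

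**What to change.** In item 3, replace *severe adverse event* with *serious or severe adverse event* in both places, with *serious* meaning the SAE term already used in item 2. Every present trigger is kept and serious UADEs of any intensity are added.

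If the sponsor confirms that *severe* was a slip, use *serious adverse event (SAE)* alone. That also removes the halt for severe but non-serious UADEs.

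The cost is a wording change in two places, filed as an IRB amendment, with no change to sample size, data collection or analysis. The downside is an occasional extra temporary pause. Under the *serious or severe* wording, the existing halt for severe but non-serious UADEs also stays.
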